## Additional details

Our primary outcome as well as secondary outcomes are convenient data points collected in the standard treatment and surveillance of postpartum anemia. As such patients will not need any study specific venipuncture or visits. The frequency and availability of appointments ensures that any symptomatic patient will quickly be seen and evaluated.

Any subject who requires escalation of treatment beyond oral or IV supplementation (blood transfusion) will be referred to receive appropriate intervention. These subjects will still be included in the intent-to-treat analysis. The routine surveillance of anemic postpartum patients described above ensures that any treatment failure will be quickly identified and addressed.

## Outcomes

Our primary outcome will be hemoglobin level at 6 weeks postpartum. Based on the available evidence we hypothesize that IV iron supplementation will be superior or at least not inferior to oral iron supplementation. Additionally, we aim to assess the secondary outcomes as listed in the introduction obtained by chart review. Data to be collected includes population characteristics including demographics and data points described in the outcomes listed under the introduction obtained by chart review.

## **4. Disposal and Administration of Drug and Placebo/Drug compliance**

The intervention drugs (IV/PO Iron and placebo) will be provided by Greenpark Compounding Pharmacy and UTMB Investigational Drug Service (IDS). The latter will receive, store and dispense the drugs for the study.

Once a qualified subject is consented and randomized, an order will be entered in Epic. The UTMB IDS will be notified to dispense the study drug according to the treatment assignment per study protocol. The assigned drug and placebo will be delivered to the nursing unit to be administered by the nurse assigned to the subject. The assigned nurse will document the administration in Epic using Medication Administration Record (MAR). Any unused study drug will be returned to IDS for documentation and disposal. Medications used in this study will not be billed to the subject or her insurance company.

The IDS will dispense the pills in a container/bottle and the subject will be given the bottle and given instructions to come to clinic at 6 weeks postpartum to see provider with bottle/container. The supplies given will be enough for total treatment of 6 weeks.

The subject will be included in the analysis by intent-to-treat once the assigned pills are dispensed from IDS and sequential number posted on the subject specific randomization form.

Drug compliance: subject will be instructed to bring pill container to all clinic visits. The provider will document number of pills in the container in order to account for compliance at best in each postpartum visit and emphasize compliance. At the end of the treatment period (6 weeks postpartum visit), the research team will collect the container and count the returned pills prior to returning it to the IDS for reconciliation within 2 weeks of receiving the bottle. Study participation will end at 6 weeks postpartum. However, if subject does not come to their scheduled postpartum visits, we will do our best to attempt to contact and retrieve drug container up to 10 weeks postpartum.

If subject misses her regular postpartum visit, we will make every effort to contact the subject by phone and enquire about the outcomes.

## **5. Criteria for Inclusion of Subjects:**

- Maternal age  $\geq$  18 years and  $<$  50 years
- Delivery at UTMB
- Hemoglobin below 9 g/dl in postpartum day 1: This population has the highest risk to have complications from postpartum anemia, protracted recovery and the most to benefit from IV iron (4 studies showed benefit of IV iron at 6 weeks PP in subjects with baseline hemoglobin values ranging from 7.4 to 8.1 g/dL.)
- Singleton gestation

## **6. Criteria for Exclusion of Subjects:**

- Enrolled in another trial that may affect outcome at the discretion of the PI
- Diagnosis of malabsorptive disorder or history of gastric bypass procedure
- Known diagnosis of anemia other than iron deficiency (thalassemia, macrocytic anemia, sickle cell, etc.)
- Significant cardiovascular disease, including but not limited to myocardial infarction or unstable angina within 6 months prior to study inclusion or current history of NYHA Class III or IV congestive heart failure
- Patient has received blood transfusion or there is a plan to transfuse
- Lactose intolerance

## **7. Sources of Research Material:**

The primary and secondary outcomes for this trial will be obtained from chart review for enrolled patients.

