**1. Introduction and Purpose:**

Postpartum anemia is a major global maternal health problem. In developing countries, postpartum anemia affects more than two thirds of women. In the United States, it affects 50% of mothers (1) and it has been linked to maternal morbidities such as impaired cognition, depression, and fatigue (2-5). Its negative impact on infant-mother bonding and neonatal care (6) has been reported. A major risk factor for postpartum anemia is iron deficient anemia in the antepartum period. The latter results from physiological changes in pregnancy; total blood volume increases by approximately 50% and red blood cell mass increases by 25% (7). The relative increase of blood volume compared to red blood cell mass causes a physiological anemia of pregnancy and therefore the hemoglobin and hematocrit threshold for diagnosing anemia in pregnancy are different than that of a non-pregnant adult. This increase in red blood cell mass, combined with the needs of the fetus, placenta, and normal anticipated blood loss from vaginal delivery represent a total additional need of 1,000 mg iron for a pregnancy, depleting maternal iron reserve (8-11). Oral iron supplementation is currently the standard of care for women with iron deficiency postpartum anemia (12,13). Up to 40% of patients do not tolerate oral iron (13), mainly due to gastrointestinal effects, leading to poor compliance and persistent anemia (14). Intravenous (IV) iron has advantages that bypass absorption challenges and may lead to faster recovery of iron stores and hemoglobin concentrations (11), with a proven safety record (16-17). Despite its advantages, IV iron is more costly and needs to be administered under supervision in a hospital or outpatient clinical setting. Two major reviews have evaluated the impact of IV iron in the postpartum period (18, 19). The first review did not find differences in maternal fatigue or maternal deaths, but did not report hematological effects such as postpartum hemoglobin. Four new randomized trials have been published comparing IV iron to oral iron therapy (20-23). An updated review of 15 randomized control trials (N=2182) concluded that hemoglobin concentrations at 6 weeks postpartum were almost 1 g/dL higher in women who received IV iron compared to oral iron (19). The safety profile of IV iron was also reassuring. Among the 15 trials included, only 2 were from the United States and neither one had 6 weeks postpartum hemoglobin as primary outcome. Hence, a large multicenter clinical trial is needed to adequately assess the impact of both modalities on hematological effects of postpartum anemia. Our aim is to perform a feasibility trial in order to guide a larger definite trial.

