#### Secondary outcomes:

- Assessment of adverse effects (such as: arthralgia, backache, chills, dizziness, moderate to high fever, headache, malaise, myalgia, nausea, and vomiting)
- Analysis of CBC indices including reticulocyte count, MCV, etc.
- Iron studies at time of diagnosis (Total Iron binding capacity, Ferritin, serum Iron levels: this panel measures the amount of iron used from the body's stored iron in contrast to reticulocyte counts that measures amount of red blood cells the bone marrow is making).
- Need for transfusion in the peripartum period
- Postpartum hemoglobin and hematocrit
- Neonatal weight
- Postpartum fatigue (multidimensional fatigue inventory (MFI) instrument validated by Smets et al.) at 6 weeks visit.
- Postpartum depression (Edinburgh postnatal depression scale) at 6 weeks visit.
- Neonatal outcomes such as NICU admission, hyperbilirubinemia, and APGAR scores
- Relationship of obesity to effectiveness of supplementation in both study arms
- Drug compliance

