#### Study Risks and Benefits:

The known risks of IV iron therapy are minimal infusion reactions: nausea, vomiting, chills, headache, flushing, constipation, mild arthralgia/myalgia of the chest or flank or facial flushing. All of these symptoms routinely abate after therapy, and plasma tryptase levels drawn after the reaction are always normal. The symptoms are most likely due to minor reactions to labile plasma iron released with any of the formulations. Compared to the side-effects present in the majority of people taking oral preparations, such as constipation, metallic taste, gastric cramping and thick green tenacious stool, the adverse events with IV iron are minor, infrequent and short-lasting. Another concern is anaphylaxis, it

has been reported to be very rare (0.6%) with the new IV iron formulation currently in use. IV iron is consequently moving rapidly forward in the treatment paradigm. Published evidence supports a wider and earlier role for IV iron in the management of postpartum anemia and raises the question of whether it should be frontline therapy in such condition.

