## Screening

All pregnant patients who deliver in our unit undergo a laboratory screen for anemia at the first postpartum day as part of the UTMB standard of care while recovering in the hospital. Eligible patients (PPD#1 patients with a hemoglobin less than 9 g/dl) will be screened and approached while inhouse (detailed under section 8).

The anticipated procedures flow is as follows

1. Research staff will go to postpartum ward.
2. Research staff will confirm with provider that possible subjects are appropriate candidates for treatment with ferrous sulfate.
3. Research staff will approach screened patients to obtain consent from possible subjects.
4. Subjects will be randomized using a computer-generated sequential randomization log with group assignment, subject name, and medical record number.
5. After patient is consented and enrolled, the provider will be notified orders will be placed in EPIC by providers with the assistance of the research staff; and a note will be placed in the electronic chart indicating that the patient is enrolled in the study.
6. Subjects will continue to receive standard, routine postpartum care and surveillance of postpartum iron anemia.
  - a. Research staff and PI will periodically monitor surveillance data by chart review.
7. During their routine 6 weeks postpartum visit, patient's hemoglobin level will be obtained (standard of care at UTMB). If subjects have a hemoglobin level drawn before the 6 weeks visits, such as in the 3 weeks postpartum visit, we will also collect this information.
8. Research staff will conduct chart review to obtain the data points for the primary and secondary outcomes (described in section 1)

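### Adverse effects come only from charts of routine care; if symptoms at home are charted less fully than those around the infusion, the whole-study comparison understates IV iron's tolerability advantage.

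*Combined protocol and SAP*

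**What the plan says.** Section 1, under Secondary outcomes, lists: "Assessment of adverse effects (such as: arthralgia, backache, chills, dizziness, moderate to high fever, headache, malaise, myalgia, nausea, and vomiting". The list is open-ended.

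The source of these data is given consistently. Section 7 states that "The primary and secondary outcomes for this trial will be obtained from chart review for enrolled patients". Section 3, Screening, step 8, repeats it: "Research staff will conduct chart review to obtain the data points for the primary and secondary outcomes". Section 3, Outcomes, again says chart review. Section 3, Additional details, describes the data as by-products of routine care: "Our primary outcome as well as secondary outcomes are convenient data points collected in the standard treatment and surveillance of postpartum anemia".

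The one provision for asking a woman directly about outcomes is in section 4 and applies only to non-attenders: "If subject misses her regular postpartum visit, we will make every effort to contact the subject by phone and enquire about the outcomes". For women who attend, section 4 has the provider record the pill count; it does not mention symptoms. Section 10 has adverse events summarised quarterly but gives no method of eliciting them.

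On setting, the Introduction says IV iron "needs to be administered under supervision in a hospital or outpatient clinical setting", and section 4 has the assigned nurse give it on the unit. The tablets go home in a bottle for 6 weeks, with routine visits at 3 and 6 weeks. On expected burden, the Introduction says "Up to 40% of patients do not tolerate oral iron (13), mainly due to gastrointestinal effects", and Study Risks and Benefits refers to "side-effects present in the majority of people taking oral preparations, such as constipation, metallic taste, gastric cramping and thick green tenacious stool". Section 12 names fewer gastrointestinal side effects as a benefit of IV iron.

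**The concern.** Both arms receive an infusion and 6 weeks of tablets, so recording is the same in the two arms at any given time. But the active drug sits in a different period in each arm: IV iron in the infusion period, when a nurse is present, and oral iron in the home period, when a symptom reaches the chart only if the woman mentions it and someone writes it down. If the second route loses more events than the first, the oral arm loses more drug-caused events than the IV arm. The same applies to any single listed symptom, such as nausea, that can occur in both periods.

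At stake is the tolerability comparison that section 12 puts forward as a reason to prefer IV iron, and the outcome rates that section 2 wants for designing the definitive trial. An effect that was never charted cannot be recovered at analysis.

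**Working it through.** The documents give no figure for adverse effects, so there is none to reproduce. They give 40 women (20 per arm), oral intolerance of up to 40%, and relative risk with 95% CI for dichotomous endpoints (section 13). Every capture rate, background rate and infusion-effect rate below is an assumption. Using 40% as the rate of any tablet effect is also an assumption, because the Introduction's figure refers to intolerance.

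Notation: *s1*, *s2* = share of affected women who are recorded in the infusion and tablet periods; *e* = infusion effect; *t* = tablet effect; *b0*, *bg* = background in the infusion and tablet periods.

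**Whole study, any adverse effect**

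IV = 1 − (1 − s1[1 − (1 − e)(1 − b0)])(1 − s2·bg)

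Oral = 1 − (1 − s1·b0)(1 − s2[1 − (1 − bg)(1 − t)])

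With e = 0.10, t = 0.40, b0 = 0.02, bg = 0.10, the IV arm's infusion-period risk is 1 − 0.90 × 0.98 = 0.118, and the oral arm's tablet-period risk is 1 − 0.90 × 0.60 = 0.46.

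| Capture, infusion / home | IV | Oral | Oral − IV (points) | RR, IV/oral |
|---|---|---|---|---|
| 100% / 100% | 0.206 | 0.471 | 26.5 | 0.44 |
| 90% / 90% | 0.187 | 0.425 | 23.8 | 0.44 |
| 90% / 60% | 0.160 | 0.289 | 12.9 | 0.55 |
| 90% / 30% | 0.133 | 0.154 | 2.1 | 0.87 |

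Equal capture leaves the relative risk essentially unchanged. Unequal capture moves it towards 1. Over e = 5–10%, t = 40–50%, b0 = 2–10% and bg = 10–20%, the recorded IV advantage is 19.6–35.8 points at 90%/90%, 10.3–22.4 at 90%/60%, and 1.1–9.0 at 90%/30%.

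If the true burden is equal (e = t = 0.10, b0 = 0.02, bg = 0.10), both arms are truly at 0.206. At 90%/30% they are recorded as 0.133 (IV) and 0.074 (oral), a false IV excess of 5.9 points.

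**Tablet period only**

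Oral = s2[1 − (1 − bg)(1 − t)]; IV = s2·bg

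Here s2 multiplies both arms and cancels in the ratio. With t = 0.40 and bg = 0.10:

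| Home capture | Oral | IV | Difference (points) | RR, oral/IV | Expected events, oral v IV (20 per arm) | Chance of no IV-arm event |
|---|---|---|---|---|---|---|
| 90% | 0.414 | 0.090 | 32.4 | 4.6 | 8.3 v 1.8 | 0.91^20 = 15% |
| 60% | 0.276 | 0.060 | 21.6 | 4.6 | 5.5 v 1.2 | 0.94^20 = 29% |
| 30% | 0.138 | 0.030 | 10.8 | 4.6 | 2.8 v 0.6 | 0.97^20 = 54% |

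The relative risk is not biased, but it rests on fewer events, and with no IV-arm event it cannot be estimated without a correction. Over t = 40–50% and bg = 5–20%, the difference falls from 28.8–42.8 points (exact Fisher power 39–87%) at 90% capture to 19.2–28.5 (21–60%) at 60% and 9.6–14.3 (7–15%) at 30%. To show the precision: 11 v 2 events is 45 points (Newcombe 95% CI 16.1 to 65.5), whereas 3 v 1 is 10 points (−11.0 to 31.4).

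**The case against.** The strongest reply is that the premise is assumed. Nothing in the documents says ward charts record symptoms better than clinic charts; section 4 has the nurse document the administration, not reactions. If clinic notes are as full as ward notes, the whole-study distortion largely disappears. Infusion effects that appear after discharge would also fall in the home period and weaken it. This stands, and it is why the point is conditional.

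A second reply is that the planned measure is the relative risk, that within a period it is unaffected, and that tabulating dated chart entries by period would remove the distortion at no cost in data collection. This also stands for the ratio. It does not restore the missing events, the risk difference or the absolute rates needed for planning, and the plan does not specify tabulation by period. Nor does the plan name a whole-study composite, but a by-arm count of a listed symptom over 6 weeks has the same structure.

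A third is that the plan has safeguards: routine visits, ready appointments for symptomatic women, phone contact and quarterly event summaries. These help, but none asks every woman the same questions.

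Finally, power is low in any case: with full capture, the first illustration has exact Fisher power of about 32% at 20 per arm. A checklist does not cure that.

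A reader might infer more than the documents support:

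- **IV iron could look worse than oral.** With the first illustration's other values, 90%/30% capture gives 0.219 v 0.154 only if the infusion effect is 20%. That is an extreme case and sits badly with the protocol's description of IV events as infrequent.
- **Phoning only non-attenders biases the comparison.** It does mix two methods, but a bias needs attendance to differ by arm (or the methods to work differently in the two arms), and the documents give no basis for assuming either.
- **Omitting constipation and similar effects from the listed symptoms is an error.** The list gives examples only.

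**Conclusion.** The point holds in conditional form. Chart review is the stated source for adverse effects, and the double dummy does not protect a whole-study comparison when the active drug falls in differently recorded periods. If home capture is lower than infusion capture, IV iron's recorded advantage shrinks, on the planned relative risk as well as on the difference. Within the tablet period, under-recording costs events, precision and absolute rates, but does not bias the relative risk.

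Lower home capture is an inference, and the size cannot be computed from the documents; the scenarios are illustrations, not estimates. It would be wrong to conclude that the tolerability result will be biased, or that the hemoglobin result is affected. This is a secondary outcome in a 40-woman feasibility trial, so the change is worth making because it is cheap, not because the trial depends on it.

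**What to change.** In section 3 (Screening, step 8) and section 7, add a second source for adverse effects. The existing blinded team or the clinic provider asks every woman the same short yes/no symptom checklist, with severity, before discharge after the infusion and at the routine 3- and 6-week visits. If a visit is missed, the same wording is used by phone. Add constipation, metallic taste, gastric cramping and stool change to the listed symptoms. Keep chart review for serious events and transfusion.

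In section 13, report women with at least one event by arm for the pre-discharge period, the post-discharge period and the whole study, as relative risk and risk difference with 95% CI, descriptively. Note that late infusion effects fall in the post-discharge period.

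The cost is an IRB amendment, some staff time and about 40 × 3 = 120 short forms, with no new visit or blood draw. The 6-week visit already includes the fatigue and depression scales and bottle collection. Direct questions will raise background rates in both arms, recall over 3 weeks is imperfect, the trial departs slightly from chart-only data, and estimates stay imprecise at 20 per arm.

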## **8. Recruitment Methods and Consenting Process:**

Patients delivered at UTMB Galveston campus will be screened to identify patients with a hemoglobin below 9 g/dl in postpartum day 1 who also satisfy the other eligibility criteria. Clinical providers will be educated about the trial prior to enrollment. We plan to identify these patients by screening the charts of patients delivered in our labor and delivery unit to identify potential subjects. Information to be reviewed as part of the screening process will be hemoglobin laboratory data and relevant exclusion and inclusion history. Research staff will function as the screeners and will alert providers that their patient is a potential subject. The provider caring for that patient will then be informed of the patient's eligibility. Research staff will work with the provider to ensure that the study intervention is appropriate therapy for the patient. If the provider agrees that the study intervention is appropriate, the provider will then approach the patient to ascertain interest in participation. If the patient is interested, the provider will introduce the research staff to the patient who will then explain the study to the patient as part of the consenting process. A screening log will be used to track all subjects approached for the study. At the time of consent and randomization, the patient will be educated as to the dosing regimen as well as the routine treatment surveillance that will occur. This will be done by the research staff consenting the patient.

### Spanish speakers:

Spanish speaking patients will be screened by use of a Spanish interpreter and all patient study materials will be translated into Spanish.

### Consenting process:

Written consent will be obtained in a private room in the hospital postpartum ward by direct person-to-person conversation. The PI or a collaborator will be responsible for the informed consent. Subjects will be given the time needed in order to fully understand and read the consent forms up to 12 hours. All efforts will be made by the research staff to answer all questions the subject has and to ascertain that the subject has the right to refuse to participate in the study. The consent form and process will describe that patients will be randomly assigned to either the study or control group. Each patient will be informed that participation is completely voluntary and in no way will affect the postnatal care they receive.

## **9. Potential Risks:**

### Randomization Risk:

Since treatment will be randomized, it is possible that one or more of the other treatment groups will have more benefit or lower side effects than the other group.

